22.5. Participant Safety Monitoring

At each site an experienced research team member will visit ALL patients at home fortnightly for safety monitoring and questionnaire-based assessments. This will include assessment of abdominal pain, vital signs, LTAD and collection of routine clinical bloods (FBC, INR, renal/ hepatic profile and CRP). The research team member will collect ascites drainage data recorded by community nurses at each site. Please see SAFETY REPORTING (section 22) for adverse event reporting.

The research team member will follow guidance in the lone worker policy when conducting home/usual place of care visits.

23. STATISTICS AND DATA ANALYSIS

23.1. Sample size calculation

Following on from the HTA Committee and PPI feedback and the International LIverHope Consortium's recommendations (73), we have selected HRQoL as our primary outcome.

The minimal clinically important difference (MCID) is the mean change in HRQoL scores for patients reporting a minimal yet perceptible change in health between the baseline and follow-up assessments. (85) In the ongoing LiverPal Study (one of the largest palliative trial in the United States (86), an MCID of 9 points on the FACT-Hep questionnaire was used; and in a study assessing LTADs in cirrhosis (87), an MCID of 10 points was chosen (SF-36 questionnaire). While these studies show the use of the MCID to inform sample size in palliative trials, neither of the tools selected are validated in advanced cirrhosis. As we will be using the SFLDQoL, a sensitive and validated questionnaire in advanced cirrhosis (34), we have selected a MCID of 8 points.

In our feasibility REDUCe study (46), the pooled baseline mean across SFLDQoL domains (excluding sex function) was 56.4 (SD=26.1). With 93 participants in each group for the analysis, we will have 90% power for 5% significance to detect an adjusted difference in mean SFLDQoL scores of 8 points between the LTAD and LVP groups at the end of 3-months (effect size 0.31). This effect size falls within Cohen's recommended cut offs for small (0.20) to moderate (0.50) effect size. (88) We will assume a correlation between baseline and the 3 follow-up measurements of 0.48 which is the lower bound of the 95% Confidence Interval for the correlation (point estimate 0.77) (from REDUCe study data). (46) With an expected 40% attrition (REDUCe study) (46), we will recruit 310 participants in total for the trial.

The MCID is the minimal change between baseline and follow up for an individual that is considered clinically important. (85) However, as this is a RCT, we want to detect a difference in means between the LTAD and the LVP groups of 8 points at end of the 3-month follow-up. Randomisation should ensure that the difference in means between the groups is zero at baseline so, by end of the follow up, the difference in means we expect to see between the groups is 8 points. As described above, we have determined our MCID through standardisation against existing literature, as far as is possible. Furthermore, through embedding a parallel qualitative study we will be able to iteratively triangulate qualitative and quantitative data – ensuring the clinical significance of our primary outcome is validated. Finally, our data will contribute to the evolution of fully validated PROMs in advanced cirrhosis cohorts, enabling robust and high-quality trials of other potential interventions.

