9.4. Primary endpoint/outcome

The primary outcome is liver specific HRQoL assessed at 3 months using the SFLDQoL questionnaire (34), the only HRQoL tool validated in advanced cirrhosis.

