23.4. Statistical Plan and Analysis

All analyses will be performed in Stata version 17.0 (89) or later. A detailed statistical analysis plan (SAP) will be written up prior to data analysis.

Summary of baseline data and flow of patients

Participant flow will be depicted according to the CONSORT 2010 Statement. (90) Baseline data will be summarised by trial group, normally distributed variables described by their means/standard deviations, skewed continuous variables by their medians/interquartile ranges and categorical variables by their frequencies/percentages. Scoring rules for the study instruments will be detailed in the full statistical analysis plan.

Primary outcome analysis

The primary outcome will be analysed, following intention-to-treat principles, using a linear mixed effects model with fixed effects for time point (2 dummy variables), gender, continuous Child Pugh score, randomisation group, randomisation group by time point interaction and adjusting for SFLDQoL score at baseline, and with a random effect for participant to handle the correlation between repeated measurements. The model will be fitted using restricted maximum likelihood estimation. We will report the estimated treatment differences between LTAD and LVP groups at weeks 4, 8 and 12, their 95% confidence intervals and p values.

Secondary outcome analysis

Secondary outcomes will be analysed using mixed effects regression models appropriate to outcome type, adjusting for baseline measure of outcome, in addition to the fixed and random effects as detailed for the primary outcome analysis.

Subgroup analyses

Analysis will be stratified to include, but not limited to, liver prognostic scores, survival, development of peritonitis, ascitic fluid albumin level and presence of informal caregivers.

Participant population

All data collected on all randomised participants will be analysed in the arm to which they were randomised.

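### The 90% power stated for the 3-month difference is about 66% at the protocol's own planning correlation of 0.48; 93 per group reproduces there only as a calculation for the mean of three follow-ups

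*Protocol*

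**What the plan says.** Section 9.4 of the protocol fixes the endpoint: "The primary outcome is liver specific HRQoL assessed at 3 months using the SFLDQoL questionnaire". Section 23.1 gives the size: "With 93 participants in each group for the analysis, we will have 90% power for 5% significance to detect an adjusted difference" of 8 points "between the LTAD and LVP groups at the end of 3-months (effect size 0.31"). The closing paragraph of that section repeats the target as 8 points at the end of the 3-month follow-up.

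The inputs are also in section 23.1. On spread: "the pooled baseline mean across SFLDQoL domains (excluding sex function) was 56.4 (SD=26.1"). On correlation: "We will assume a correlation between baseline and the 3 follow-up measurements of 0.48", which it identifies as the "lower bound of the 95% Confidence Interval for the correlation (point estimate 0.77"). On inflation: "With an expected 40% attrition (REDUCe study) (46), we will recruit 310 participants in total for the trial".

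Section 23.4 specifies a linear mixed model adjusted for baseline, with a group-by-time interaction and one random effect per participant. On reporting it says: "We will report the estimated treatment differences between LTAD and LVP groups at weeks 4, 8 and 12". It defines no average effect over follow-up.

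**The concern.** A mean of three follow-ups is less variable than one follow-up, so a sample size that suits the mean is too small for a single visit. A model with a full group-by-time interaction estimates the week-12 difference separately. With complete data, that contrast gains nothing from weeks 4 and 8. If 93 was derived for the mean, the 90% is attached to a quantity the protocol does not name as primary.

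At stake is how a null result would be read. A non-significant week-12 difference in a trial described as having 90% power looks like evidence against an 8-point benefit. If the actual power is nearer two thirds, it is much weaker evidence.

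**Working it through.** **Inputs (section 23.1).** Difference 8; SD 26.1; effect size 0.31 as rounded, 8/26.1 = 0.3065 unrounded; baseline/follow-up correlation 0.48; three follow-ups; 93 analysed per group; attrition 40%. Two assumptions are added: a two-sided 5% test (sidedness is not stated), and a value for the correlation among follow-ups, which is not given.

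**Formula.** For ANCOVA with one baseline, n per group = 2(1.960 + 1.2816)² × f / ES² = 21.015 × f / ES², where f is the variance factor. SE = SD × √(2f/n), and power = Φ(8/SE − 1.960).

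**Step 1: reproduce 93 and 310.** For the mean of three follow-ups with all correlations 0.48:
- f = (1 + 2 × 0.48)/3 − 0.48² = 0.6533 − 0.2304 = 0.4229
- n = 21.015 × 0.4229 / 0.31² = 92.5, so 93; power at 93 is 90.2%
- 186 / (1 − 0.40) = 310
- with 8/26.1 unrounded, n = 94.6, so 95; power at 93 is 89.5%

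Other methods tried at correlation 0.48 give, per group: unadjusted comparison 219-224, change score 233, mean of follow-ups without baseline adjustment 143-147, single-visit ANCOVA 169-173. Averaging with follow-ups correlated 0.77 instead of 0.48 gives 135-138. None gives 93.

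**Step 2: the week-12 difference with 93 completers per group.**
- f = 1 − 0.48² = 0.7696
- SE = 26.1 × √(2 × 0.7696/93) = 3.36
- power = Φ(8/3.36 − 1.960) = 66% (67% with the rounded effect size)
- difference detectable with 90% power = 3.2416 × 3.36 = 10.9 points
- n for 90% power at 8 points = 168.3 (ES 0.31) or 172.1 (8/26.1), so 169-173 analysed per group
- after 40% attrition, 338/0.6 to 346/0.6, about 564-577 in total

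**Step 3: vary the baseline correlation (8/26.1, 93 per group).**

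| Correlation | f = 1 − ρ² | SE | Week-12 power |
|---|---|---|---|
| 0.48 | 0.770 | 3.36 | 66% |
| 0.60 | 0.640 | 3.06 | 74% |
| 0.70 | 0.510 | 2.73 | 83% |
| 0.77 | 0.407 | 2.44 | 91% |

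**Step 4: let the mixed model use early data from drop-outs.** Take 155 randomised per group, 93 of them complete, and two assumed retention patterns: a steady loss to about 87%, 73% and 60% at weeks 4, 8 and 12, or all 62 losses between weeks 8 and 12. Generalised least squares under data missing at random, baseline correlation 0.48, gives week-12 power of:
- follow-ups correlated 0.48: 68% and 69%
- follow-ups correlated 0.77: 74% and 78%

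**Step 5: the average as the target, 93 completers per group, all correlations 0.48.** SE = 26.1 × √(2 × 0.4229/93) = 2.49.
- Constant 8-point effect from week 4: power 90% (89.5%).
- Effect growing linearly to 8 points at week 12 (2.67, 5.33, 8): the mean is 5.33, and power = Φ(5.33/2.49 − 1.960) = 57%.

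**The case against.** The strongest reply is that 0.48 is deliberately cautious. It is the lower 95% confidence limit, and at the point estimate of 0.77 the week-12 contrast has 91% power with the same 93 per group. That stands, and it limits what can be claimed. A reader might infer that the trial is underpowered, or that a true 8-point benefit would be missed one time in three. The documents do not support that as a general statement, because it describes the lower-limit scenario only. What does not stand is the 90% as written, since the protocol attaches it to 0.48. For week 12, 90% is reached only near the point estimate, so the margin that 0.48 appears to provide is not there.

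A reader might also infer that the protocol reports having averaged the follow-ups. It does not. The inference rests on the match to 93 and 310, on the reference to three follow-up measurements, on an assumed common correlation of 0.48 and on the rounded effect size. The week-12 shortfall at 0.48 does not depend on it.

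Nor is 66-69% a complete range at baseline correlation 0.48. It assumes follow-ups correlated 0.48 with each other. A higher correlation among follow-ups, combined with partial data, takes it to about 78%, still short of 90%. Adjustment for gender and Child-Pugh score could add a little, but the protocol gives no figure for this. A one-sided 5% test would give only 77-78% with 93 completers.

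A SAP could define the contrast more closely, but the power figure and its time point are stated in the protocol itself.

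**Conclusion.** The concern holds in this form: the 90% in section 23.1 is not the power for the protocol's own primary quantity at its own planning correlation. With 93 completers per group, SD 26.1 and a two-sided 5% test, week-12 power is about 66% at 0.48 and reaches about 91% only at 0.77. Using partial follow-up gives about 68-69% at 0.48 throughout, or about 74-78% if follow-ups correlate 0.77 with each other. These last two ranges rest on assumed retention patterns and on data missing at random.

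That the 93 came from averaging is a well-supported inference, not something the protocol states. The finding is a wrong power statement. It does not show that 310 participants are too few whatever the true correlation.

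**What to change.** Keep week 12 as the primary time point. In section 23.1, replace the unqualified 90% with week-12 power across the plausible correlations: about 66-69% with all correlations 0.48, 74% at 0.60, 83% at 0.70 and about 91% at 0.77. State the correlation assumed among follow-ups, whether the figure counts completers only or also partial follow-up, and whether the test is two-sided. The cost is a change of text and a less favourable figure; recruitment need not change. The sponsor should see that this accepts lower power at 0.48, since 90% for 8 points at week 12 would take about 564-577 randomised.

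An optional alternative is to make the average difference over weeks 4, 8 and 12 the primary contrast, with week 12 as a key secondary. That is more than a wording change. It replaces the primary endpoint in the study summary, section 9.4 and Table 2, and must be fixed before any outcome data are seen. It gives about 90% power only if the 8-point effect is roughly constant from week 4 and follow-ups correlate about 0.48; if the effect grows linearly to 8 points, power is about 57% with 93 completers per group.

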23.2. Internal pilot

An 18-month internal pilot will assess recruitment and LTAD safety: 12 months recruitment, three months' follow up, one-month for analysis, two-months' for a STOP/GO decision. We will recruit 48 patients to allow estimation of recruitment rate & retention with a margin of error of 15% assuming 60% retention. With an expected rate of one patient recruited per site every 4 months, this could be achieved with 24 sites (2 sites opened each month) over 12-months' recruitment. During the final follow up, analysis & STOP/GO decision period of the internal pilot, recruitment (n=36) would continue in the pilot sites in preparation for the main trial.

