23.2.1. Progression criteria for stop/go

RED: end trial; AMBER: explore methods for increasing recruitment/improving LTAD safety and with permission of funder proceed with protocol revisions; GREEN: continue to main phase of trial.

	RED	AMBER	GREEN *
Pilot recruitment/total study recruitment target by end of study month 21	<10%	10-20%	≥21%
Mean recruitment rate/site/month (based on data to end of study month 21)	<0.2	0.2-0.3	>0.3
Number of sites opened by end of study month 18	<19	20-23	≥24
Total number of patients recruited by study month 21	<55	55-65	≥66
Proportion of those recruited by study month 18 retained to end of follow up*	<50%	50%-60%	>60%
Percentage of LTADs removed due to peritonitis by end of study month 21*	>15%	10%-15%	<10%
Proportion completing SFLDQoL questionnaire (except questions on sexual function) in those retained at time point, by end of month 18*			
Baseline	<90%	91%-95%	>95%
Week 4	<85%	85%-90%	>90%
Week 8	<80%	80%-85%	>85%
Week 12	<75%	75%-80%	>80%
Checklist for LTAD insertion and post procedure monitoring % completed	<75%	75%-85%	>85%

Table 6. Progression Criteria for Pilot Stop/Go

* Based on feasibility study data (46), and systematic review (44)

Assuming a successful pilot, we will then open an additional 11 sites over the next 5 months, recruiting the remaining 226 patients from a total of 35 sites over 26 months of the main trial (on average about six patients/site). This is consistent with our feasibility study recruitment (36 patients recruited across five sites over 30 months). The first eight sites, which will be open the longest, will recruit 11 patients on average; the final seven, 6 on average, over a total recruitment period of 44 months.

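### The pilot's 48 patients, and the GREEN count of 66 built on it, fit the planned rate only if every site is credited with a patient on opening; Table 6's recruitment rows match neither that rate nor each other

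*Protocol*

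**What the plan says.** Section 23.2 sets the pilot size for precision: "We will recruit 48 patients to allow estimation of recruitment rate & retention with a margin of error of 15% assuming 60% retention". It then argues feasibility, starting from this "expected rate of one patient recruited per site every 4 months, this could be achieved with 24 sites (2 sites opened each month"), within a 12-month recruitment period. Over the next six months, "recruitment (n=36) would continue in the pilot sites in preparation for the main trial".

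Section 23.2.1 (Table 6) has three rows that score recruitment to study month 21:

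- Share, "Pilot recruitment/total study recruitment target by end of study month 21": RED <10%, AMBER 10-20%, GREEN ≥21%.
- Mean rate per site per month: RED <0.2, AMBER 0.2-0.3, GREEN >0.3.
- Count, "Total number of patients recruited by study month 21": RED <55, AMBER 55-65, GREEN ≥66.

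RED is labelled as ending the trial. Below the table, 11 more sites open over 5 months and 226 patients remain. "The first eight sites, which will be open the longest, will recruit 11 patients on average; the final seven, 6 on average", over 44 months in total. The plan is said to agree with the feasibility study's 36 patients from five sites in 30 months.

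**The concern.** Sites open gradually, so most of the 24 are open for only part of the 12 months. Multiplying the time they are open by one patient per 4 months falls well short of 48. The count row of Table 6 builds on the 48, and the whole-trial projection uses the same counting. If the planned rate is meant as an average, a pilot that opens every site on time and recruits at that rate would be scored against a target it was never expected to reach. The stop/go reading would then reflect the counting rule, not a recruitment problem.

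**Working it through.** **Inputs (sections 23.2 and 23.2.1).** Two sites open per month for 12 months; one patient per site per 4 months (0.25 per site-month); then 11 sites over 5 months, taken as 2, 2, 2, 2, 3; 44 months in total; target 310. Assumption: study month 18 is recruitment month 12, so study month 21 is recruitment month 15. The protocol does not say this. It is inferred because all 24 sites are due by study month 18 and 66 = 48 + 24 × 0.25 × 3.

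**Step 1: reproduce the plan.** Give each site a patient at opening and another every 4 months, so a site open for t months contributes t/4 rounded up.

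- Month 12: 8 × 3 + 8 × 2 + 8 × 1 = 48.
- Month 15: 66. Month 18: 84 = 48 + 36, leaving 310 − 84 = 226.
- Month 44: 8 × 11 + 8 × 10 + 8 × 9 + 4 × 7 + 7 × 6 = 310, with 11 each for the first eight sites and 6 each for the last seven.

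Every stated figure is matched.

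**Step 2: the same inputs as an average rate.** Expected patients = 0.25 × open site-months. The range runs from opening at the start of each month to opening at its end.

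| To recruitment month | Site-months | Expected at 0.25 | Plan | Average rate the plan needs |
|---|---|---|---|---|
| 12 | 156-132 | 39-33 (mid-month 36) | 48 | 0.31-0.36 |
| 15 | 228-204 | 57-51 (mid-month 54) | 66 | 0.29-0.32 |
| 44 | 1186-1151 | 297-288 | 310 | 0.26-0.27 |

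For month 12, 2 × (12 + 11 + … + 1) = 156, and end-of-month opening removes 24. For month 15, add 24 × 3 = 72. For month 44, the first 24 sites give 924 and the last 11 give 262; end-of-month opening removes 35.

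Once all 24 sites are open, both readings add 24 × 0.25 = 6 patients a month. The gap at months 12 and 15 is therefore the same 9-15 patients, all of it from crediting a patient at opening.

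**Step 3: which reading the protocol supports.** The feasibility comparison is an average: 36 / (5 × 30) = 0.24 per site-month if all five sites were open throughout. Rounding up as in step 1 would give 5 × 8 = 40 for that study. Table 6 also scores a mean rate per site per month.

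**Step 4: put the three rows on one scale.** Patients by study month 21, with all sites opened on schedule (204-228 site-months):

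| Row | RED below | GREEN from |
|---|---|---|
| Share of 310 | 0.10 × 310 = 31 | 0.21 × 310 = 65.1, so 66 |
| Mean rate | 0.2 × (204 to 228) = 41-46 | above 0.3 × (204 to 228) = 61-68 |
| Count | 55 | 66 |

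The GREEN lines roughly agree and the RED lines do not. A count of 55 is 55/228 to 55/204 = 0.24-0.27 per site-month and 55/310 = 17.7%, AMBER on both other rows. The planned 0.25 is itself AMBER on the rate row.

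**Step 5: chance of each count-row reading.** With Poisson counts at means of 51 to 57, P(<55) runs from 69% down to 38% and P(≥66) from 2% up to 13%. At the plan's own mean of 66 they are about 8% and 52%.

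**The case against.** The strongest reply is that 48 contains no arithmetic error. A reader might infer that it cannot follow from its inputs, or that the section mixes two rules because the later 36 equals 24 × 6 × 0.25 exactly. Neither inference is supported. One schedule, a patient at opening and one every 4 months, gives 48, 36, 66, 226, 11, 6 and 310, and it is a possible literal reading of the stated rate. A trial following it exactly reaches 66, which is GREEN on the count row. That stands.

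The consequences are also limited. Section 23.2 justifies 48 by precision and says only that it could be achieved. Table 6 does not say how its rows combine, AMBER allows revision, and under section 23.3 the data are assessed descriptively, with a DSMC recommendation to the TSC. On the average-rate reading the whole-trial shortfall is modest. At 60% retention, 288-297 recruits give 86-89 analysed per arm instead of 93. Taking the stated 90% power at 93 as given, Φ(3.24 × √(n/93) − 1.96) is about 88-89%.

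The reply does not remove two points. The convention is nowhere stated and allows no start-up lag: the two sites opened in month 12 are credited with two patients in at most one month, against 0.5 at 0.25 each. And the mismatch between the RED lines in Table 6 holds under either reading.

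**Conclusion.** The concern holds as an undisclosed assumption and a set of inconsistent decision thresholds, not as a miscalculation. The 48 and 66 match the planned rate only if each site recruits on opening. As an average over open time, which is how Table 6 scores recruitment and how the feasibility rate is cited, the plan gives 33-39 and 51-57. The planned 0.25 is AMBER on the rate row, and the RED count line lies well inside AMBER on the other two rows.

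A reader might go further and conclude that a trial running to plan would probably read RED or AMBER on the count row and be stopped. The document does not support that. The 38-69% chance of RED and 2-13% chance of GREEN apply only to the average-rate reading, and a single RED row is not said to end the trial. What is supported is that recruitment at the planned average rate could be read as failure.

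The month-21 figures rest on the inferred study-month mapping, on all sites opening on schedule and on the rate row being taken per month that a site is open.

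**What to change.** Recompute the projection from site-months and choose one of two statements:

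- Keep 0.25 as the average rate and restate expected recruitment as about 36 (33-39) by recruitment month 12 and about 54 (51-57) by study month 21.
- Keep 48, 66 and 310, and state the average rates they require: 0.31-0.36, 0.29-0.32 and 0.26-0.27 per site-month.

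In either case, state whether a patient is counted at site opening and how study months map to recruitment months. Then reset the count, share and rate rows of Table 6 so that they express the same RED, AMBER and GREEN boundaries, before the stop/go review.

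The cost is a few sentences and the recruitment rows of one table, with no change to trial procedures. The drawback is a less favourable stated projection: either fewer expected pilot patients or a higher required rate.
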